1 BACKGROUND AND RATIONALE

1.1 Study Synopsis

Toxicities related to pediatric cancer treatment can lead to significant illness, organ damage, treatment delays, increased health care cost, and decrease in quality of life. Such toxicities are largely due to tissue damage sustained by chemotherapy, and strategies designed to limit such cellular damage to normal tissues may reduce therapy-related morbidity and mortality. In addition to their *in vitro* and *in vivo* anti-cancer effects, naturally occurring soy isoflavones have anti-inflammatory and anti-oxidant properties, and have been shown to reduce side effects of therapy in adult oncology clinical trials. This study will examine the effect of genistein, the major isoflavone component in soybeans and the most extensively studied of the soy isoflavones, on short-term side effects of myelosuppressive chemotherapy in pediatric cancer patients. Subjects will be randomized to receive either: a) 30 mg genistein daily throughout chemotherapy Cycles 1 and 2 and placebo during chemotherapy Cycles 3 and 4; or b) placebo daily during chemotherapy Cycles 1 and 2 and 30 mg genistein daily during chemotherapy Cycles 3 and 4. We hypothesize that subjects will have fewer short-term therapy-related side effects during cycles of chemotherapy given in conjunction with genistein supplementation than cycles given with placebo.

1.2 Background

1.2.1 Toxicities Associated With Chemotherapy for Pediatric Cancers

While cure rates for pediatric cancers have steadily improved over the last several decades, toxicities associated with cancer therapy continue to cause significant morbidity and mortality [1, 2]. Serious side effects of chemotherapy and radiation are common and are thought to be due to a variety of factors, including depletion of glutamine and glutathione, free radical generation, cytokine release, and oxidative damage [1, 3-9]. Unlike certain targeted anti-cancer agents, most chemotherapeutic drugs have nonspecific mechanisms of action that damage both normal tissue and cancer cells [1]. Similarly, the mechanism of action of radiation is nonspecific and can cause oxidative DNA damage to normal tissues that are within the radiation field [1]. These nonspecific effects of chemotherapy and radiation tend to be more severe in tissues that contain rapidly dividing, mitotically active cells such as those found in the bone marrow [1]. Myelosuppressive regimens cause a predictable decline in peripheral blood cell counts, usually 7 - 10 days after exposure to therapy. Highly-suppressed absolute neutrophil counts during this period put patients at an elevated risk for serious infection [10]. The standard of care at most institutions is to admit neutropenic patients with fever to the hospital and treat with empiric intravenous broad-spectrum antibiotics until their febrile neutropenia resolves. This is due to the high mortality associated with serious bacterial infections in this population, reported to be around 1% [11, 12]. Such patients also often require packed red blood cell and platelet transfusions for chemotherapy-induced anemia and thrombocytopenia, respectively, which are

associated with hemolytic transfusion reactions and transfusion-transmitted infections. Other common acute toxicities due to cancer treatment include mucositis caused by chemotherapy and radiation as well as neurotoxicity due to vincristine and other tubulin-inhibiting chemotherapeutic agents [13-15].

Many long-term side effects of therapy cause significant morbidity and mortality [2]. One problematic long-term side effect of therapy is the irreversible ototoxicity due to platinum-based chemotherapy [16, 17] that is estimated to occur in up to 61% of patients receiving cisplatin and postulated to be due to cochlear oxidative damage [3-5, 16]. Ototoxicity negatively impacts patients' quality of life by impairing their social and cognitive function and overall development [5]. It can also indirectly lead to increased risk of cancer recurrence if the cumulative dose of cisplatin is significantly reduced due to ototoxicity [5]. Cardiac toxicity caused by anthracycline-induced oxidative damage is another common dose-limiting side effect of therapy [18, 19]. Up to 40% of patients who receive anthracyclines will have an abnormal echocardiogram and survivors of childhood cancers who were treated with anthracyclines have a 15-fold increased relative risk of congestive heart failure compared to adults who were not treated for a childhood cancer [2]. Such therapy-related toxicities significantly impact patients' quality of life and cause treatment-related mortalities. Therapies that limit normal tissue damage without negatively impacting the therapeutic effects of chemotherapy and radiation are needed to improve outcomes and quality of life for childhood cancer patients.

1.2.2 Anti-cancer/Anti-Inflammatory Effects of Soy Isoflavones

Soy isoflavones are naturally-occurring components of soybeans that have both anti-neoplastic and antioxidant properties. Their *in vitro* and *in vivo* anti-cancer effects have been tested in varied cancer model systems and include apoptotic induction [20, 21], growth inhibition [22-24], cell cycle regulation [25], and sensitization to chemotherapy [26, 27] and radiation [28]. Soy isoflavones inhibit growth in preclinical studies of multiple pediatric solid tumors, including Wilms, rhabdoid renal tumors, and neuroblastoma [20-22, 24], as well enhance the cytotoxicity of chemotherapy in medulloblastoma cells [27].

One mechanism by which soy isoflavones exert a protective effect is by inhibiting oxidative damage in healthy cells [29-31]. Oxidative DNA damage is significantly reduced in men and women who receive soy milk supplementation, as determined by 8-isoprostane plasma levels and DNA strand breakage [32-34], which is consistent with *in vitro* and *in vivo* experiments demonstrating antioxidant properties of isoflavones [35-37]. Isoflavones also reduce hydrogen peroxide-induced DNA damage in sperm [38] and neutrophils [39].

Of the three main soy compounds, genistein, daidzein, and glycitein, the major component in soybeans (about 50%) and the most extensively studied of the soy isoflavones is genistein [40]. Genistein has been shown *in vitro* to increase antioxidant gene expression in colon cancer [41] and inhibit induced oxidative stress in epidermal

carcinoma [37, 42] and terminally differentiated leukemia [37]. It also inhibits oxidation of low density lipoprotein in the presence of copper ions and superoxide free radicals, and protects vascular endothelial cells from damage by oxidized lipoproteins [43]. In an experimental model of acute liver damage, genistein-treated rats had lower liver tissue malondialdehyde levels, higher levels of glutathione, and reduced inflammation and necrosis compared to rats that were not exposed to genistein. The protective effect correlated with reduced markers of lipid peroxidation, suggesting that genistein inhibits reactive oxygen species-induced membrane damage [44]. Genistein administration is associated with increased activity of several antioxidant enzymes, including superoxide dismutase, glutathione peroxidase, glutathione reductase, catalase, and glutathione-S-transferase in a mouse model [45]. Additionally, in a guinea pig asthma model, genistein treatment was associated with fewer total white blood cells (WBCs) and eosinophils in bronchoalveolar lavage fluid and reduced airway eosinophilia. Subsequent experiments demonstrated decreased eosinophil peroxidase activity and epidermal growth factor-induced tyrosine phosphorylation, suggesting mechanisms for genistein-mediated inhibition of inflammation [46]. Interestingly, several preclinical studies suggest that genistein may have opposing mechanisms of action and biological effects on some paired normal and malignant cell lines. For example, it has little impact on the generation of reactive oxygen species in astrocytes or hyperdiploidy in normal breast cell models, but they increase in paired malignant cell lines [37, 47]. These and other paired *in vitro* models show a minimal or pro-survival impact of genistein in non-malignant cells but poorer survival in their cancerous counterparts [47-52].

While genistein may promote inflammatory processes, including increased IFN- γ secretion, in the context of some cancers [62-64], data suggest that soy isoflavone consumption may lower pro-inflammatory proteins in non-malignant cells. *In vitro* studies suggest a mechanism whereby genistein may attenuate homocysteine inflammatory signaling through IL-1 β , reactive oxygen species, and NF- κ B, thereby inhibiting expression of C-reactive protein and its downstream effectors, IL-6 and TNF- α [53-56]. Supporting this, genistein supplementation was associated with reduced serum IL-6 and IFN- γ in a mouse autoimmune encephalitis model [57]. Soy intake inversely correlated with serum TNF- α , IL-6, and IL-1 β levels in rats [58], which is consistent with data showing lower serum IL-6 and TNF- α levels in Chinese women who consumed soy-rich diets [59]. Serum CRP and homocysteine levels have been found to be inversely related to soy isoflavone intake in U.S. adults [60, 61]; CRP also inversely correlates with serum genistein levels in adults receiving flavonoid supplementation [60]. Inhibition of cytokine production may be another mechanism by which soy isoflavones, and specifically genistein, reduce inflammation in healthy tissues.

1.2.3 Genistein Reduces Chemotherapy-Induced Side Effects

Genistein's anti-inflammatory and antioxidant properties may counteract the oxidative damage and inflammation induced by anti-neoplastic therapy in healthy tissues, thereby reducing untoward toxicities. Adult men with localized prostate cancer who received 200 mg daily soy isoflavone supplementation (including about 96 mg genistein per day)

concomitant with their radiation therapy had reduced urinary, intestinal, and sexual adverse effects compared to subjects treated with placebo. Compliance was 100% with the study tablets and no side effects from soy supplementation were reported [28]. A small pediatric pilot study found a similar reduction in chemotherapy and radiation therapy-related toxicities with genistein supplementation [65]. In this study, eight solid tumor and brain tumor patients received the first course of therapy without soy supplementation and then received a 0.3 g tablet containing 82% soy isoflavone extract and 2.7% (8 mg) genistein daily with subsequent courses of chemotherapy. No isoflavone-related toxicities were noted and none of the children stopped taking the supplement. While these data were not statistically significant, subjects receiving genistein in conjunction with chemotherapy appeared to have less myelosuppression, less mucositis, shorter durations of antimicrobial therapy, and fewer blood product transfusions compared to cycles of chemotherapy without genistein. Furthermore, subjects who received abdominal radiation reported less pain and diarrhea while taking the genistein supplement, although this was also not statistically significant. While encouraging, these data are preliminary and additional randomized trials are needed to evaluate genistein's effect on anti-neoplastic therapy-related toxicities.

1.3 Study Design and Rationale

Although recent studies have demonstrated the ability of genistein supplementation to reduce chemotherapy-related acute toxicities in a limited number of pediatric cancer patients, data regarding safety and efficacy of soy isoflavones in pediatric cancer patients are scant. The purpose of this study is to evaluate the efficacy and safety of genistein supplementation in pediatric cancer patients receiving myelosuppressive chemotherapy. The study plans to accrue 44 eligible subjects at University of Virginia (coordinating center) and additional participating sites (affiliates).

Genistein safety, efficacy, pharmacokinetics, and pharmacodynamics have been determined in adult clinical trials [66,67]. While much of the soy isoflavone data does not specify which of the soy components are responsible for the clinical effects seen, genistein is known to be the major component in soybeans (about 50%) and the most extensively studied of the soy isoflavones [40]. This study will employ purified genistein rather than a mixture of soy components so as to more clearly define genistein's safety and efficacy in the context of myelosuppressive chemotherapy and a pediatric population.

A dose of 30 mg purified genistein was chosen for this clinical trial based on prior safety and efficacy studies in pediatric and adult populations. In a study of eight solid and brain tumor pediatric patients, subjects received a 0.3 g tablet containing 82% soy isoflavone extract and 2.7% (8 mg) genistein daily [65], which corresponded to a daily genistein dose of approximately 130 mg. No isoflavone-related toxicities were observed and no subjects discontinued supplementation during that study. The findings support the safety of genistein supplementation at a dose up to 130 mg in a pediatric population. In addition, De Ruijter and colleagues [68] recently studied the effects of genistein in 30

subjects with Sanfillipo disease with a median age of 11 – 13 years. They demonstrated that genistein could be administered in this population at doses of 10 mg/kg/day with no observed treatment-related adverse events (AEs). The safety of soy isoflavones in the pediatric population has been evaluated by researchers studying the effects of soy formula intake in infants. Infants who were exposed to an estimated 4 to 16 mg/kg/day of soy isoflavones (approximately 2 to 8 mg/kg/day of genistein, which is equal to about 32 mg daily for a 4 kg infant) in soy formula during their first 4 months of life had no evidence of any significant short- or long-term deleterious effects, including no differences in puberty or fertility compared to infants receiving cow's milk formulas [71]. A dose of 30 mg genistein has been established as a minimal effective dose in adults; it demonstrated elevated serum levels of genistein and was associated with reduced prostate-specific antigen levels in adults with prostate cancer [69, 70]. Most AEs were mild and significant events were rare in those studies. Together, toxicity data do not suggest a need for a dose-finding pediatric trial or that the dose of purified genistein selected for this study will compromise the safety of pediatric subjects. As a reference, two eight-ounce glasses of soy milk contain roughly 30 mg of genistein.

Eligibility is limited by a patient's intended chemotherapeutic regimen. Qualifying regimens must be known to be myelosuppressive and have at least four cycles (14 or 21-day cycles). The sequence of protocol therapy will be randomized in a double-blind fashion to control for bias. This study will also employ a crossover design to limit any period effects and to allow for intra-subject comparisons. Efficacy will be retrospectively evaluated using clinical laboratory results and the incidence of pre-specified AEs. Subjects will be monitored for safety starting on Cycle 1 Day 1 through 30 days following the last day of genistein supplementation.

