
Methodology: This is a multi-center, randomized, double-blind, placebo-controlled crossover study to evaluate the effect of the isoflavone genistein on the short-term untoward effects of myelosuppressive chemotherapy used to treat pediatric cancers. Newly diagnosed cancer patients aged 1 - 21 years will be registered to the study and informed consent will be obtained prior to any study-related procedures. Stratification will be based on length of chemotherapy cycles: 14 days or 21 days. Subjects will be randomized 1:1 to one of two schedules within each stratum:
 
Arm A: Subjects will receive genistein daily throughout chemotherapy Cycles 1 and 2, and placebo during chemotherapy Cycles 3 and 4
 
Arm B: Subjects will receive placebo daily throughout chemotherapy Cycles 1 and 2, and genistein during chemotherapy Cycles 3 and 4
 
The safety and efficacy of genistein will be assessed during each cycle through clinical laboratory tests, cytokine panels, and physical exams. Study supplement compliance will be monitored by use of a subject diary, drug reconciliation, and serum isoflavone levels. Adverse events will be monitored starting on Cycle 1 Day 1 through 30 days following the last day of study supplementation (genistein/placebo). Serious adverse events will be collected through 6 months post-study intervention.
	
Number of subjects (planned): Up to 50 subjects will be accrued to obtain 44 eligible subjects.	

Main Eligibility Requirements:
 
Inclusion criteria:
 
 New diagnosis of a solid tumor or lymphoma, with histologic verification of malignancy Age 1 - 21 years at the time of diagnosis Able to tolerate enteral medication administration Performance score minimum requirement ≥ 50 on Karnofsky/Lansky scale Planned chemotherapy regimen involves at least four consecutive cycles of chemotherapy that is known to be myelosuppressive 
Exclusion criteria:
 
 Known allergy to soy or any soy-based food or supplement Pre-existing neutropenia or neutrophil qualitative or quantitative disorder Pre-existing cytopenia or bone marrow failure syndrome Subject will not receive myelosuppressive chemotherapy Current acute or chronic leukemia diagnosis Enrolled on another therapeutic or supportive care clinical trial within the last 30 days Secondary malignancy 	

Investigational intervention:

- Genistein: 30 mg/day, oral tablets
- Placebo: oral tablets

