3.1 Inclusion Criteria

- [1] Newly diagnosed solid tumor or lymphoma with histological verification
- [2] Age 1 - 21 years at time of diagnosis
- [3] Karnofsky/Lanksy performance score of ≥ 50
- [4] Able to tolerate enteral medication administration
- [5] Planned chemotherapeutic regimen for a patient must meet **all** of the following criteria:
 - a. A known myelosuppressive regimen which includes at least two of the following agents: actinomycin, carboplatin, cisplatin, cyclophosphamide, daunorubicin, doxorubicin, etoposide, ifosfamide, topotecan
 - b. At least four consecutive cycles
 - c. Cycle length is either 14 or 21 days
 - d. Regimen **must either alternate myelosuppressive chemotherapeutic agents in an X-Y-X-Y format**, such that the same chemotherapy is given every other cycle (e.g. vincristine/doxorubicin/cyclophosphamide | ifosfamide/etoposide), **or repeat the same chemotherapeutic agents each cycle in an X-X-X-X format** (e.g. repeated cycles of cisplatin/etoposide/bleomycin). Courses eligible for this trial may occur at any time during treatment provided that they are consecutive and follow the one of the described patterns. Non-myelosuppressive anti-neoplastic treatments will not be considered for the purposes of determining eligibility. Questions regarding whether or not a patient's chemotherapy plan meets inclusion criteria will be decided by the Study Chair.
- [6] Informed consent or parental permission and assent obtained prior to trial-related activities ([Section 4.3](#))
- [7] Able and willing to comply with all study related procedures
- [8] Women of childbearing potential must agree to use adequate contraception prior to study entry and for the duration of study participation. Should a woman become pregnant or suspect she is pregnant while participating in this study, she should inform her treating physician immediately.

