4.7.2 Genistein/Placebo Supplementation

For the purposes of this study, the duration of treatment cycles will coincide exactly with chemotherapy cycles. "Cycle 1" here refers to the first chemotherapy cycle during which the subject receives genistein or placebo, though this may not be the actual first cycle of the subject's chemotherapeutic treatment.

Subjects will receive 30 mg genistein (Arm A) or placebo (Arm B) daily throughout Cycles 1 & 2, beginning on the first day of the first cycle of chemotherapy coinciding with this study (Cycle 1 Day 1) and ending two days prior to the predicted start date of Cycle 3. Following a 2-day washout, subjects will then receive placebo (Arm A) or 30 mg genistein (Arm B) throughout chemotherapy Cycles 3 & 4, beginning on the first day of Cycle 3 and ending on the last day of Cycle 4. **The treatment schedule is summarized on Roadmaps, located in the Procedure Manual appendices.** For the purposes of this clinical trial, “study supplement” will refer to both genistein and placebo.

The study supplement will be delivered orally by the subject or a parent, and a diary will be kept to document dose administration. For doses given at home, subjects and parents will be instructed to bring unused pills to study visits. For children who are unable to swallow tablets, instructions for crushing and administering will be given to the families (Procedure Manual). Tablets may be crushed and delivered via feeding tube only if subjects are unable to take the medication orally and the feeding tube terminates in the stomach. Delivery to the duodenum or jejunum may alter genistein pharmacokinetics.

Subjects will record study treatments on a daily Pill Diary to indicate number of doses and time of dosing (Procedure Manual). If a subject misses a dose by less than 12 hours, he or she must be instructed to take the missed dose. If a subject misses a dose by more than 12 hours, he or she must be instructed to skip the missed dose and continue with regular dosing schedule. However, he or she must redose if vomiting occurs within the first 20 minutes after study supplement ingestion. Redosing may occur only once per 24 hour period.

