6.2.1 Medical History and Physical Examination

A medical history must be obtained and physical exam performed during the Pre-treatment Assessment to establish baseline medical condition(s) ([Section 6.2](#)). Medical history includes clinically significant diseases, history of cancer (including date of diagnosis, location of disease, stage, grade, biopsies, resections, prior cancer therapies and procedures), and selected medications (anti-neoplastic agents, blood products, soy products, antimicrobials, and G-CSF) used by the patient within 28 days prior to protocol therapy (genistein/placebo).

A full physical examination will be performed at the Pre-treatment Assessment and Day 1 of each cycle ([Sections 6.2](#) and [6.3](#)). Physical examinations will include examination of the following body systems: general appearance/constitution (including height and body weight), skin, neck, HEENT (head, ears, eyes, nose and throat), cardiovascular system (auscultation of heart sounds), lungs/chest (auscultation of lung fields), abdomen palpation, genitourinary system (auscultation of bowel sounds), lymph nodes, extremities, and nervous system.

An abbreviated, symptom-directed physical exam will be performed at all other visits ([Section 6.3](#)). This must also be conducted in such a way to assess for incidence of secondary conditions listed as endpoints (i.e., infection, mucositis, etc.) In addition, any clinically significant abnormal finding which was not noted at the baseline assessment must be reported as an AE, provided it also meets the reporting criteria in [Section 9](#).

Baseline conditions and AEs must be reported as diagnoses, when possible. Laboratory value abnormalities present at the time of enrollment must be reported as baseline conditions according to their CTCAE classifications. The baseline onset and severity of all grades of all target AEs defined in [Section 6.2](#) must be reported, as well as any other

non-target baseline condition if its severity is greater than or equal to grade 3 ([Section 9.1.8](#)). The outcome of baseline conditions and resolution dates, when applicable, must be reported at the end of the follow-up period.

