8.2 Sample Size and Accrual

This pilot study is designed to obtain preliminary data to describe the overall pattern of ANC over time during myelosuppressive chemotherapy, assess neutropenia, and to determine whether the data support a decrease in time to recovery of 3 days for the genistein group compared to placebo. Target sample size for this pilot study was based upon results from a chart review performed at UVA which found that the mean day of recovery for pediatric cancer patients receiving myelosuppressive chemotherapy was day 16.25. Group sample sizes of 22 eligible subjects per group achieves approximately 80% power to detect a difference of 3 days with a 5% one-sided Mann-Whitney-Wilcoxon Test. These results were based on 3000 Monte Carlo samples assuming a null Poisson (mean 16.25) distribution and an alternative Poisson (mean 13.25) distribution. ANC determination and neutropenia are defined in Sections 6.3 and 7.1. Adjusting for a 10% ineligibility/drop-out rate, approximately 49 - 50 subjects may need to be accrued to the study.

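### The parallel Cycle 1–2 comparison neither stratifies on nor adjusts for chemotherapy given before study Cycle 1, which may cost co-primary endpoint (a) some precision

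*Combined protocol and SAP*

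**What the plan says.** **Design.** Section 1.3 gives the reason for the crossover: "This study will also employ a crossover design to limit any period effects and to allow for intra-subject comparisons".

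**Entry point.** The Synopsis (Methodology) states: "Newly diagnosed cancer patients aged 1 - 21 years will be registered to the study". Inclusion criterion 1 (Section 3.1) also requires a new diagnosis, but neither passage fixes the entry cycle. Criterion 5d says "Courses eligible for this trial may occur at any time during treatment provided that they are consecutive" and follow one of two permitted regimen patterns. Section 4.7.2 defines Cycle 1 as the first cycle given with study supplement, "though this may not be the actual first cycle" of the patient's chemotherapy.

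**Endpoint and analysis.** Section 8.1 sets two co-primary endpoints: (a) average day to recovery over Cycles 1 and 2, compared between arms, and (b) the within-subject difference between genistein and placebo cycles. Section 8.3 stratifies on cycle length only. The one test named for day of recovery is in Section 8.2, a "5% one-sided Mann-Whitney-Wilcoxon Test". Section 8.4 names repeated measure models and Cochran–Mantel–Haenszel tests but no covariate.

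**Data available.** The baseline history in Section 6.2.1 already covers "prior cancer therapies and procedures".

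**The concern.** The crossover controls differences between subjects only where each subject serves as their own control, which is endpoint (b). In endpoint (a) each subject contributes to one arm. Two subjects both labelled study Cycle 1 may have had different amounts of earlier myelosuppressive treatment, so a study-cycle term in a repeated measure model does not capture that exposure.

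If earlier exposure changes the day of recovery, it adds between-subject variance to (a). It can also be unevenly split by chance with 22 subjects per arm. It is fixed before randomisation, so adjusting for it is legitimate. At stake are a few points of power and the steadiness of the A–B estimate, not the validity of the test.

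**Working it through.** **1. The plan's own figure.** Section 8.2: "Group sample sizes of 22 eligible subjects per group achieves approximately 80% power to detect a difference of 3 days", "assuming a null Poisson (mean 16.25) distribution and an alternative Poisson (mean 13.25) distribution". Simulating that test (20,000 replicates) gives power of 0.797 with continuity correction and 0.801 without. Accrual is 44 / (1 − 0.10) = 48.9, so 49. Both stated figures reproduce.

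A formula that can be worked by hand: mean variance V = (16.25 + 13.25)/2 = 14.75, SD 3.84. With rank-test efficiency 0.955, the effective n per arm is 22 × 0.955 = 21.01, and

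power = Φ(3 / √(2V/21.01) − 1.645) = Φ(2.532 − 1.645) = 0.812.

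**2. Assumed inputs.** The documents give no prior-cycle effect, no direction and no distribution of entry cycles. Assume a share q = 0.3 or 0.5 of later entrants whose recovery day differs by d days, with this variance added to the planned Poisson variance.

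- Added variance = d²q(1 − q)
- SD of the chance shift in the A–B difference = d√(2q(1 − q)/22)

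| d (days) | Added variance | Share of total variance | SD of chance shift (days) | Unadjusted power, formula in step 1 |
|---|---|---|---|---|
| 0 | 0 | 0 | 0 | 0.812 |
| 1 | 0.21–0.25 | 1–2% | 0.14–0.15 | 0.807–0.808 |
| 2 | 0.84–1.00 | 5–6% | 0.28–0.30 | 0.790–0.793 |
| 3 | 1.89–2.25 | 11–13% | 0.41–0.45 | 0.762–0.770 |
| 4 | 3.36–4.00 | 19–21% | 0.55–0.60 | 0.726–0.739 |

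Example, d = 3 and q = 0.5: added variance 9 × 0.25 = 2.25; V = 17.00; share 2.25/17.00 = 13%; chance-shift SD 3 × √(0.5/22) = 0.45; power Φ(3/√(34/21.01) − 1.645) = 0.762.

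**3. Simulated, unadjusted rank test against rank ANCOVA with a yes/no covariate.** Unadjusted power is about 77–79%, 74–76% and 71–75% at d = 2, 3 and 4, against 79–80% adjusted. The gain is about 1–2 points at 2 days and about 4–8 points at 3–4 days. At 1 day the loss of about half a point in the table is cancelled by the degree of freedom spent. With no effect, adjustment costs under 1 point. Differences of a point or so are near Monte Carlo error and should not be leaned on.

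**4. A linear effect per prior cycle, as a cross-check.** With prior cycles uniform on 0–4, unadjusted power is 0.78, 0.75 and 0.64 at 0.5, 1 and 2 days per cycle. With 0–2 prior cycles it is 0.80, 0.79 and 0.74. ANCOVA on the count stays near 0.81.

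**5. If the planned variance already contains the spread.** Then unadjusted power remains about 80%. In the normal approximation without the rank factor, Φ(3/(3.84√(1 − R²)√(2/22)) − 1.645), power rises from 0.83 to 0.845, 0.86 and 0.895 when prior cycles explain R² = 5%, 10% and 20% of the variance.

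**6. Type I error.** Simulated at 4.9% with 0–4 prior cycles and 1 day per cycle, so it stays nominal.

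**The case against.** The strongest reply is that randomisation already makes (a) valid, (b) removes stable between-subject differences, and adjusting for one prognostic factor in a 44-subject pilot is a preference about efficiency. That stands, and it caps the importance of the point.

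Every magnitude input is assumed, and differences of 2–4 days are large beside the 3-day target. The documents also narrow the spread. New diagnosis is a binding criterion, and exclusions 3 and 4 in Section 3.2 remove pre-existing neutropenia and cytopenia. They do not fix cumulative exposure. The chart review behind the mean of 16.25 does not state its mix of cycles, so step 5 may be the better description. Endpoint (a) also averages two cycles. If those were independent Poisson counts (an assumption), unadjusted power would be 87–96% over the same grid.

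A reader might infer from Section 1.3 that the plan expects recovery to change with cycle number and then ignores this. The sentence does not support that. It is general design language about any period effects, gives no direction or size, and concerns periods within the study rather than treatment before it.

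What survives is an asymmetry: under 1 point of power lost if prior cycles do not matter, several points recovered if they matter a good deal.

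**Conclusion.** The gap is real but modest and confined to co-primary (a). Entry at a later chemotherapy cycle is allowed, and nothing in Sections 8.2–8.4 accounts for it. Under the additional-variance assumption the loss is negligible at a 1-day difference and reaches several points of power only at 3–4 days. A 2-SD chance imbalance would then shift the estimate by about 0.8–1.2 days (2 × 0.41 to 2 × 0.60). If the planned variance already covers the mix of entry cycles, there is no loss against the stated 80%, only a gain forgone.

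Two stronger readings are tempting: that (a) is biased, or that the stated power is wrong. Neither holds. Allocation is randomised, type I error is nominal, and the power figure reproduces on its own inputs. This is an optional improvement, not a correction of an error.

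**What to change.** Before unblinding:

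- Derive one baseline variable from the Section 6.2.1 history: no myelosuppressive cycle before study Cycle 1, against one or more.
- Pre-specify it, together with the cycle-length stratum, in a rank ANCOVA for the Cycle 1–2 comparison and in the between-group repeated measure models.
- Tabulate it by arm.

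Fix the test and the coding now, because a covariate chosen after an imbalance is seen would be data-driven. Rank ANCOVA is preferable to a Wilcoxon test stratified on both factors, which risks sparse strata with 44 subjects.

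The cost is one derived field and one degree of freedom for the new covariate. No visits, tests, subjects or clinical procedures change.
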